The biopsies taken at the colonoscopy and biopsies from the specimen removed at surgery will be analyzed for Ki67 and cleaved caspase-3 expression through immunohistochemistry (please see below in the "methods" section).

The study participants are randomized to metformin or placebo at the time of preoperative examination. Eligible patients will receive metformin or placebo 500 mg once a day for two days, followed by 500 mg twice a day for two days and then 500 mg three times a day until 10 days after the operation (visit at the out-patient clinic). The treatment is discontinued at the day of surgery and recommenced afterwards with the first meal. The patients will after surgery receive 500mg three times a day again. In summary patients will receive metformin or placebo for 20 days before the operation and again 10 days after the operation.

[figure not shown]

Figure 1: Study course

If a participant withdraws the consent then the participant will leave the study. In case of severe medical emergency (e.g. stroke or severe sepsis) which results in emergency surgery, stay in an intensive care unit, or hospitalization before the planned operation, the patient is excluded from the study. No further data will be collected from these patients after leaving; however, previous collected data will be part of the final data analysis in an intention to treat analysis. If a patient needs a CT scan with intravenous contrast in the treatment period the medication will be stopped.

Each year around 170 patients with colon cancer are undergoing surgery at Slagelse Hospital. In total 48 patients are needed for the study and we expect an inclusion rate of 50%. Approximately 15% are diagnosed with diabetes and are not eligible for the study. The inclusion of patients is therefore expected to last for 8 months. Subsequently, there will be a 4 month time period for data analysis and manuscript preparations. The study will be initiated in the fall of 2017.

RANDOMIZATION, ALLOCATION, CONCEALMENT AND BLINDING

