All samples in the biobank, blood and tumor will be destroyed after 10 years, and participants can have them destroyed earlier, should they wish so.

INTERVENTION

The study medicine will be produced by Teva with each pill containing 500 mg metformin in a quick release preparation. The metformin tablets will be over-encapsulated in a gelatine capsule in order to make identical placebo. This will be performed by the regional pharmacy of The Capitol Region of Denmark who will also produce the placebo. The placebo will be comparable to study medication except for the active substance and will also consist of a over-encapsulated tablet. The content and chemical composition of metformin and the placebo can be seen in the individual product fact sheets. Pills will be packaged in white Duma cans with a total of 100 pills for each patient. Attached to the Duma can is a, for the purpose designed label, containing the relevant study medication information as well as the identification number for the patient. Metformin has a half-life of approximately 3 hours⁴⁸. When a participant for any reason is terminated in the study the patient will be monitored for side-effects for 24 hours.

The patients' regular medication will not be affected by the current study and patients should take their regular medication as usual.

As mentioned earlier the regional pharmacy will handle the whole randomization process, and handling of medicine before the trial. An independent person from the regional pharmacy (mentioned in the Trial Master File) on the basis of the randomization-list will apply the randomization-code and patient number on the Duma cans. Likewise, batch numbers for the metformin and placebo will be noted on a separate piece of paper correlated to the patient's number. This will all be performed in accordance to "Good Manufacturing Practice" by relevantly trained staff. The randomization-list and the list containing the batch-numbers will be stored by this independent person at a locked box at the regional pharmacy of The Capitol Region of Denmark. The sponsor/investigator will receive two set of code-envelopes from the central pharmacy. Sponsor/investigator does not have immediate access to the medicine or the randomization list, but in case of serious adverse events (SAE) access can be made. In case of urgent need of code breaking this can be performed using the code-envelopes as previously described.

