The patients are randomized to metformin or placebo at the time of preoperative examination. Eligible patients will receive metformin or placebo 500 mg once a day for two days, followed by 500 mg twice a day for two days and 500 mg three times a day for the rest of the period except the day of surgery where the medication is paused.

To establish the medicine compliance and the cumulative dosage, pill counts of study medication will be performed at the time of operation and at the visit in the out-patient clinic after surgery. The patient will be asked to bring study medication (empty, open and unopened containers) and missing pill number will be noted in the patient case report form (CRF). The aim of compliance is 75 %. Data on all patients will be

analysed according to the intention to treat principle. Per protocol analyses will be performed on data from participants with a compliance of 75 % or higher.

RISKS, SIDE-EFFECTS AND INCONVENIENCE

Metformin is a safe drug, and the side effects are primarily dose-dependent and limited to mild gastrointestinal symptoms like loss of appetite, diarrhea, vomiting, nausea and mild abdominal pain. Any adverse events will be monitored by weekly contact and graded using Common Terminology Criteria for Adverse Events version 4.0⁴⁹. The participants will be monitored for adverse events from when they start the medication until postoperative day 10 when they have finished the medication. To minimize the side-effects, the dose of metformin is slowly increased, and metformin will be withheld in participants who experience intolerable side-effects until these subside. Afterwards the participants are recommenced at 500 mg daily, followed by 500 mg twice a day.

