Throughout the trial both the sponsor/investigator, who informs the patient and the patient herself, will be blinded. Furthermore, the pathologist who performs the immunohistochemistry and cell count as well as the investigator working with the cancer cell lines will also be blinded. A code breach will occur if an unexpected event arises which demands urgent treatment where there is a reasonable probability of an adverse reaction related to the study medication. Code breach is possible for investigators in case of emergencies and the principal investigator is available day and night via phone.

The summary of product characteristics (SPC) for metformin will be appended to this document in the form of the product resume of metformin produced by Teva. It will function as reference document in evaluation of adverse events.

All adverse events will be registered and reported to The Danish Medicines Agency and the local ethics committee in the final report. All serious adverse reactions (SAR's) will be reported to the local ethics committee in an annual report together with a report on patient safety. All serious adverse reactions (SAR) will be reported to The Danish Medicines Agency in an annual report together with a report on patient safety. The SPC for metformin will be used to judge whether a serious adverse reaction is expected/unexpected and thereby a possible sudden unexpected serious adverse reaction.

The principal investigator (EC) will make sure that all information about sudden unexpected serious adverse reaction, that are lethal or life-threatening will be registered and reported to The Danish Medicines Agency and the regional ethical committee as soon as possible and at the latest 7 days after investigator has received knowledge of such a reaction. At the latest 8 days after this reporting investigator will inform The Danish Medicines Agency of the follow-up. All other sudden unexpected serious adverse reactions (SUSAR) will be reported to The Danish Medicines Agency and the regional ethical committee at the latest 15 days after investigator has gained knowledge of these. In these situations the patient will be followed until the reaction has terminated – either via contact with the investigator or via the outpatient clinic at the hospital.

Definitions of events, side-effects, unexpected side-effects and adverse reactions are as follows.

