- Adverse event (AE): any adverse event in a patient or clinical investigation subject in a clinical trial with administration of a drug whether or not the adverse event is considered related to the drug.
- Adverse reaction (AR): All noxious and unintended responses to an investigational compound at any dose.
- Unexpected adverse reaction (UAR): a side effect the nature or severity is not consistent with the applicable product information (SPC for metformin)
- Serious adverse event (SAE) or Serious Adverse Reaction (SAR): an event or effect that at any dose results in death, is life-threatening, requires hospitalization or prolongation of existing hospitalization, results in persistent or significant disability or incapacity, or is a congenital anomalous or malformation.

ETHICS

Most malignancies have linear or exponential growth models, and onset of symptoms is often preceded by a long asymptomatic phase with increasing degeneration. The accelerating growth and degeneration is what theoretically makes diagnosis-to-treatment delays especially harmful in cancer. Treatment delay is likely to take place during a critical phase with high tumor growth rates, which increase the risk of metastasis. Colon cancer is a slow-growing cancer and is in most cases a result of the adenoma-adenocarcinoma sequence⁵³, which can take up to 15 years from onset to eventual progression to malignancy.⁵⁴

Treatment delay in colon cancer has previously been controversial; however an American study showed that treatment delay was not associated with worse cancer outcomes for patients with colon cancer even in "high-risk" patients including patients with tumor positive lymph nodes, metastatic disease, extramural vascular invasion and comorbid inflammatory bowel disease⁵⁵. Furthermore, a Danish study showed that treatment delay of at least 60 days had no impact on survival from coloncancer.⁵⁶

Treatment delay, defined as the time lapse between diagnosis and surgery is described in the standardized cancer program⁵⁷ ("kræftpakkeforløb") by the Danish Health Authorities and must not be more than 10 days. In the present study we wish to expand the treatment delay to 21 days in order to be able to

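### The rules for safety data after a patient leaves the study are incompatible, and the plan does not provide for recording the outcome of a serious event still open at exit

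*Combined protocol and SAP*

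**What the plan says.** Four places in the combined protocol and SAP bear on this.

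- **STUDY PARTICIPANTS** describes two ways out. The first is withdrawal: "If a participant withdraws the consent then the participant will leave the study". The second is a severe medical emergency, with stroke and severe sepsis as examples, where after emergency surgery, "stay in an intensive care unit, or hospitalization before the planned operation, the patient is excluded from the study". For both groups: "No further data will be collected from these patients after leaving". Data gathered before leaving stay in the intention-to-treat analysis.
- **INTERVENTION** states the drug's elimination, "Metformin has a half-life of approximately 3 hours", and then: "When a participant for any reason is terminated in the study the patient will be monitored for side-effects for 24 hours".
- **RISKS, SIDE-EFFECTS AND INCONVENIENCE** sets the general window: "The participants will be monitored for adverse events from when they start the medication until postoperative day 10". It does not say what happens to that window when a patient leaves.
- **DATA AND ADVERSE EVENTS** sets the reporting times for unexpected serious reactions and continues: "In these situations the patient will be followed until the reaction has terminated". Serious reactions in general go into an annual report, and all adverse events go into the final report. No duration of follow-up is given for serious reactions that are not unexpected. The definitions at the end of that section count an event or reaction as serious if, among other criteria, it "requires hospitalization or prolongation of existing hospitalization".

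**The concern.** Each rule is understandable alone, but they overlap in the patient for whom safety information matters most. Someone admitted before surgery with a serious event may be removed from the study because of that event. From then on one section collects nothing, another gives one day, and a third requires follow-up to the end, but only if the reaction is unexpected.

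What is at stake is the completeness of the safety record. Adverse events are to be graded by CTCAE and all of them reported at the end. If an event is still running at exit, later worsening, resolution or death may never reach the trial database. The trial has no Data Monitoring Committee, so the investigators' own follow-up carries more weight.

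**Working it through.** No design figure is involved and the plan states none to reproduce. The check is a comparison of the text, with two small sums.

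**Step 1. Can one event be both serious and the reason for exit?** Yes. Hospitalisation is a criterion for seriousness (definitions in DATA AND ADVERSE EVENTS). A severe emergency leading to hospitalisation before the planned operation is a ground for exclusion (STUDY PARTICIPANTS).

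**Step 2. Which rules apply after exit?**

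| Patient who leaves | STUDY PARTICIPANTS | INTERVENTION | DATA AND ADVERSE EVENTS |
|---|---|---|---|
| Excluded for an emergency that is an unexpected serious reaction | no further data | 24 hours | follow until it ends |
| Excluded for an emergency that is an expected serious reaction | no further data | 24 hours | no follow-up stated |
| Excluded for an emergency that is a serious event not attributed to the drug | no further data | 24 hours | no follow-up stated |
| Consent withdrawn | no further data | 24 hours | follow until it ends, only if an unexpected serious reaction is open |
| Terminated for another reason | not covered | 24 hours | follow until it ends, only if an unexpected serious reaction is open |

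In the first row all three rules apply and cannot all be followed. In the second and third rows two rules conflict, and neither reaches the end of an event that lasts longer than a day.

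**Step 3. Does another section fill the gap?**

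- The general adverse-event window and the 30-day call with journal review (STUDY PARTICIPANTS) are both timed from surgery. Neither is said to continue after exit.
- In RISKS, SIDE-EFFECTS AND INCONVENIENCE, withholding the drug until side-effects settle is a dosing rule for those who continue. It does not require an outcome to be recorded.
- DATA COLLECTION AND HANDLING covers the use of data already held when a patient withdraws, not new data.

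**Step 4. How different is the follow-up?** A patient who completes has about 20 + 10 = 30 days of treatment-period monitoring (20 days before surgery and 10 after), plus the 30-day call. A patient removed for an emergency has 0 to 24 hours after exit, depending on which section prevails, unless the reaction is unexpected and serious.

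**Step 5. What does the 24 hours correspond to?** 24 h / 3 h = 8 half-lives, and 0.5^8 = 0.0039, so about 0.4% of the drug remains. The window fits drug elimination. Nothing ties it to the end of a reaction.

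**The case against.** The best defence is that the three rules serve different purposes. The 24 hours can be read as a washout check, which the half-life sum supports. The stop on data collection stands beside the intention-to-treat statement and may be meant for efficacy data. Unexpected serious reactions have their own rule. On that reading the defect is mainly silence about expected serious reactions after exit. This is a possible intention, but the stop is worded without any exception for safety data, and a site that followed it literally would collect none.

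Several parts of the defence do stand, and they rule out stronger readings that a reader might infer:

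- **That the serious event itself goes unrecorded.** It does not. It occurs before exit, earlier data are kept, all adverse events are registered, and serious reactions are reported annually. The steering committee also meets specially for a serious event. Only the later course is unprovided for.
- **That the most serious events always have the shortest follow-up.** Unexpected serious reactions are to be followed until they end. The definitions also treat a known reaction as unexpected when its severity departs from the product information, so the uncovered class is narrower than it first appears.
- **That a particular number of patients is affected.** The plan gives no rate of exit for serious events. It describes the drug's side-effects as primarily mild and gastrointestinal, and it excludes impaired kidney function and severe liver disease.
- **That the comparison of harm between arms is biased.** A missing outcome does not change the count of events by arm, and no between-arm test of harm is specified.
- **That lactic acidosis is the uncovered case.** This depends on whether the product information lists it, and that text is not in the documents. The protocol itself calls the risk very low.

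**Conclusion.** The concern holds as an inconsistency between sections with a specific gap. STUDY PARTICIPANTS, INTERVENTION and DATA AND ADVERSE EVENTS cannot all be followed for a patient removed because of an unexpected serious reaction. For an expected serious reaction, or a serious event not attributed to the drug, no section provides for follow-up to its end after exit.

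Its size is a loss of information on course, final grade and outcome for serious events open at exit, with 0 to 24 hours of collection in place of the window that continuing patients have. The number of such patients is unknown and may be very small. The primary Ki67 analysis is not affected.

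The conclusion rests on two readings of the text: that the stop on data collection means all data, as worded, and that the promise to follow a reaction until it ends refers to the unexpected serious reactions in the sentences just before it. It does not depend on what the product information lists. The point is worth acting on because following the protocol literally would lose safety data, and the remedy is cheap.

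**What to change.** Reconcile STUDY PARTICIPANTS, INTERVENTION, RISKS, SIDE-EFFECTS AND INCONVENIENCE, and DATA AND ADVERSE EVENTS in one amendment:

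1. State that the stop on data collection does not apply to safety data on serious events open when a patient leaves, unless the patient withdraws consent to follow-up.
2. State whether follow-up until a reaction is over also covers expected serious reactions.
3. State how the 24-hour monitoring and the general adverse-event window relate to these rules once a patient has left.
4. State for how long such events are followed. The sponsor should set this. The existing 30-day call is timed from surgery, so it gives no ready anchor for a patient who leaves before the planned operation.

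The means are already in the protocol: telephone contact (STUDY PARTICIPANTS) and access to patients' journals (DATA COLLECTION AND HANDLING). The cost is the amendment wording and a telephone and journal check for the patients concerned. No new procedure or sample is needed.

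### Does the 75% per-protocol cut-off need a stated pill count and denominator?

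*Combined protocol and SAP*

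**What the plan says.** The INTERVENTION section says how compliance and cumulative dosage are established: "pill counts of study medication will be performed at the time of operation and at the visit in the out-patient clinic after surgery". Missing pills are entered in the CRF. The compliance aim is 75%, all patients are analysed by intention to treat, and "Per protocol analyses will be performed on data from participants with a compliance of 75 % or higher". DATA AND STATISTICAL ANALYSIS repeats intention to treat and adds nothing on the per-protocol set.

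The schedule is two days at one capsule, two days at two, then "500 mg three times a day for the rest of the period except the day of surgery where the medication is paused". STUDY PARTICIPANTS gives 20 days before and 10 days after the operation; METHODS calls the 20 days a maximum.

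Two provisions interrupt that schedule. Under RISKS, SIDE-EFFECTS AND INCONVENIENCE, "metformin will be withheld in participants who experience intolerable side-effects until these subside", and then "Afterwards the participants are recommenced at 500 mg daily, followed by 500 mg twice a day". Under STUDY PARTICIPANTS, "If a patient needs a CT scan with intravenous contrast in the treatment period the medication will be stopped". Neither says how the affected days count towards compliance.

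**The concern.** A percentage needs a numerator and a denominator, and the cut-off sentence gives neither. With two counts available, an analyst could use the pre-operative count or the whole course. The primary outcome is Ki67 in tissue removed at surgery, so capsules taken afterwards cannot affect it. Yet a whole-course figure would let them decide who is in the set.

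The interrupted patient is harder. The restart sentence gives no length for either step and does not mention a return to three capsules a day, so the directed number of capsules cannot be rebuilt from the text. If withheld capsules stay in the denominator, someone who followed every instruction may be dropped from a set called per protocol. The protocol describes metformin's side-effects as mainly dose-dependent, so such removals might be commoner in the metformin arm. That would be a selective exclusion. A definition chosen late could also follow sight of the results.

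**Working it through.** **Uninterrupted patient.** Inputs are the schedule in INTERVENTION and the 20 and 10 days in STUDY PARTICIPANTS.

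- Scheduled before surgery: 2×1 + 2×2 + 16×3 = 54. Cut-off: 0.75 × 54 = 40.5, so 41 capsules; 13 may be missed.
- For a shorter pre-operative period of n days (n at least 4): 2 + 4 + 3(n − 4) = 3n − 6. This can be worked out from each patient's own dates.
- After surgery, assuming ten full days: 10×3 = 30. Whole course: 54 + 30 = 84; cut-off 0.75 × 84 = 63. The drug restarts with the first meal after surgery, so the 30 is approximate.

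**Does the choice of count matter?** Yes, on paper. On the whole-course figure, 33/54 before surgery (61.1%) with 30/30 after gives 63 and is in. Full intake of 54/54 before with 8/30 after gives 62 and is out. For an outcome fixed at surgery, that argues for the count at operation, which is already planned.

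**Could the denominator be the pills dispensed?** INTERVENTION says "Pills will be packaged in white Duma cans with a total of 100 pills for each patient". This describes packaging, and nothing links it to compliance. Full intake would be 54/100 at operation, so nobody would qualify. It is not a credible reading.

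**Interrupted patient.** The documents give no hold or restart lengths, so those below are assumptions. Let the hold start on day d (day 5 or later), last h days, and be followed by a days at one capsule, then two a day to day 20. Every directed capsule is taken.

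- Taken before the hold: 6 + 3(d − 5) = 3d − 9.
- Taken after it: a + 2(21 − d − h − a).
- Total: d + 33 − 2h − a, as long as the once-daily step ends by day 20.

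The last two rows assume instead that three a day resumes after two days at two a day. The loss is then 3h from the hold, 2×2 at one a day and 2×1 at two a day, which is 3h + 6.

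| Hold | Once daily | Then | Capsules taken | Start days below 41 |
|---|---|---|---|---|
| 1 day | 1 day | two a day to surgery | 30 + d | 5–10 |
| 2 days | 2 days | two a day to surgery | 27 + d | 5–13 |
| 4 days | 2 days | two a day to surgery | 23 + d to day 15; 40 on day 16 | 5–16 |
| 2 days | 2 days | two days at two, then three | 54 − 12 = 42 for days 5–15, more later | none |
| 3 days | 2 days | two days at two, then three | 54 − 15 = 39 for days 5–14; 40 on day 15; 41 on day 16 | 5–15 |

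In the second row the result runs from 32/54 (59.3%) on day 5 to 40/54 (74.1%) on day 13; day 14 gives 41/54 (75.9%) and is in. In the fourth row 42/54 is 77.8%; in the fifth 39/54 is 72.2%. On capsules directed, all these patients are at 100%.

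**Size.** The documents give no rate of withholding or of contrast CT, so the number of patients affected cannot be derived. Each is 1/24 = 4.2% of an arm.

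**The case for a change.** The strongest case for a change is that the remedy is cheap and the ambiguity is genuine. Two or three sentences written before the analysis would fix the count and the treatment of directed pauses. Later, the choice might be made with results in view. The plan keeps investigators blinded until the data have been analysed and interpreted, so allocation could not steer the choice, but blinding alone does not stop a definition being picked after the results are seen. That much stands.

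The rest is weaker. A larger loss in the metformin arm is an inference: the protocol calls the side-effects mild and gives no frequency of withholding. Describing interrupted patients as wrongly excluded presumes that per protocol means obeying instructions. The pill counts also serve cumulative dosage, and a set meant to show adequate exposure may reasonably leave out patients who received little drug. Selective exclusion is a general limit of per-protocol sets, whichever denominator is chosen. The CRF is not among the documents, and adverse events are followed by weekly contact, so the dates of a hold may well be on record.

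**Conclusion.** The gap in wording is real, but no change to the plan follows. For outcomes fixed at surgery, an analyst would take the count at operation and divide by the capsules scheduled to that patient's surgery: 54 over 20 days, with 41 needed. The plan supplies what is needed for that.

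Only the handling of protocol-directed pauses remains open. It can move an individual patient across 75%, under hold and restart lengths that the documents do not give. Both ways of counting are defensible, and reporting which one was used is ordinary practice. The per-protocol analysis is supplementary to intention to treat on all patients, which does not depend on this definition.

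How the restart sentence fits with the general schedule is for the investigators to reconcile. It is a clinical matter on which nothing is proposed here.
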